We will use Thematic Analysis, an evaluative deductive approach to analyse the qualitative focus group and interview data, as described by Clarke and Braun [77]. The SC will code each transcription and one of the researchers will code every third transcription, grouping the codes into themes and sub-themes. An iterative process will be used within the research team to define the main themes and emerging models related to the study aims. In this way thematic analysis will be reflexive to aid in identification of any instances where the PI's beliefs may unduly influence identification of these main themes.

Quantified feasibility outcomes: activity, compliance, and adverse event monitoring

Participants will record daily performance of home exercises prescribed by the treating therapist in an activity-log (yes/ no, minutes of exercise per day) to determine treatment compliance. Non-attendance at scheduled treatment sessions will be recorded by the treating therapist (yes/no per session) as well as any adverse reactions to treatment (number). Participants will complete an exiting questionnaire to assess patient satisfaction [78].

Experimental Outcomes:

Experimental outcome measures (experimental studies a. & b.) will include but are not limited to:

Category	Exploratory OM
Cervical Spine	

Kinematic Assessment - Virtual Reality	Total range of motion (deg) Peak Velocity – Rotation R (deg/s) Peak Velocity – Rotation L (deg/s) Peak Velocity – Rotation Ext. (deg/s) Global head motion accuracy (deg)
Muscle Function (CFET)	Total time (sec)
Manual Spinal Examination	Pos/ neg
Sensorimotor Function (JPE)	Degrees Error (deg) Neck Disability Index (tot/ 50) Headache Impact Test-6
Vestibulo-Ocular	
VNG OM Assessment	Full Assessment (≥ 2 pos/neg overall (pos/neg) ; pos/neg per assessment)
VOMS assessment	Increase in symptoms (11- point NRS) ; avg NPC > 5cm Dizziness Handicap Index
Participant Outcomes	
Physical Activity : Actigraphy	Minutes of Vigorous Physical Activity, min/day Physical Activity (TAC/d; steps/d; PAEE - kcal/kg/day) Activity log Consensus Sleep Diary PROMIS sleep questionnaires IPAQ (METs) Fatigue Severity Scale
Quality of Life	EuroQol-5D-5L (EQ VAS)

Data Management

Clinical data will be entered directly into the study's online data recording form which only the PI, SC and members of the research team will be able to access. Data in this form will be stored under a unique identifier generated during the initial screening session with the SC. Where raw data requires further analysis, it will be deidentified (VR and VNG outcomes) and routinely uploaded to the PIs (OG) password protected laptop or the password protected study laptop. Data collected using VR and VNG will be collected on the devices using the participants unique identifier.

Statistical Analysis

Descriptive analyses will be performed on sociodemographic data. Exploration of central tendency of all data will be evaluated using Kolmogorov-Smirnov and Shapiro-Wilk tests. Where data is significantly skewed, attempts will be made to transform using suggested methods [57]. Individual demographic variables (sex, age, BMI, IPAQ score) which could reasonably be expected to influence quantitative outcomes will be analysed for significance using univariate linear regression and included in models.

Objective 1:

Quantified feasibility outcomes: activity, compliance, and adverse event monitoring

- a. Descriptive statistics will be used for recruitment frequency and the number of eligible participants, the drop-out rate, and degree of missing data for the patient rated and clinical outcomes measures. The programme will be considered feasible if 80% of patients complete the programme until formal discharge based on the physiotherapists' assessment and treatment documentation.
- b. Adherence to the intervention by auditing and summarising patients' logbooks and the physiotherapists' assessment and treatment documentation. The SC will audit the documentation. Adherence will be considered acceptable if 80% of exercises had been recorded in the patient's logbooks.
- c. Adverse events from the treatment will be determined by auditing the physiotherapists' assessment and treatment documentation as well as inclusion of formal reports submitted to the study or HEC in the event of serious adverse events. Number of events will be considered.
- d. Patient satisfaction score (/12) from the patient satisfaction exiting questionnaire will be calculated and mean and 95% CI will be reported.

Triangulation of qualitative (analysis described above) and quantitative outcomes [79] will determine overall feasibility of using the SPE to inform treatment management.

Objective 2:

Linear mixed method analysis of repeated experimental outcomes will determine treatment effect. Effect modifiers including sex and age as well as statistically significant demographic confounders will be included in the final model. Further secondary analysis may be undertaken using data collected at all time points. Multivariable linear regression will identify items of the VOMS which best predict VNG OM.

Data storage:

All data (including patient and health practitioner data) will be stored on the personal password-protected laptops of the PI ([name]) and or the password-protected study laptop. Any hard copies of the questionnaires and consent forms will be stored in the PI's office in a secure filing cabinet. Only the researchers mentioned in the application and the SC (tba) responsible for processing and analysis will have access to the de-identified data collected during the study. The principal researcher ([name]) and the SC will keep a list identification codes with participant names, so that participants can be identified by their coded data if needed.

A standardised hard copy of the summary report of the participants findings from the screening session completed by the SC will be provided to the treating physiotherapist (via postal mail). This will not be de-identified since it will be used by the treating physiotherapist to inform treatment. A copy of these reports will be kept on the PI's personal password-protected laptop.

The treating physiotherapist will record the clinical assessment and treatments, as required, on their usual practice management systems as well as information related to study feasibility.

All data will be stored for the duration of the study on the primary investigator's password-protected University laptop and will be accessible by members of the research team. It will also be stored for at least 10 years in the school's archive folder on the High-Capacity Storage System (HCSS). Any personal information held about the participants (such as contact details and hard copy questionnaires) may be destroyed at completion of the research. Coded study information may be kept by the University of Otago in secure, cloud-based storage indefinitely. All storage will comply with NZ I data security guidelines.

Potential problems: (medical/legal; issues with disclosure; conflict of interest, etc)

The study will be led by the PI, directly supported by the SC. Regular team meetings (face-to-face where possible) will be held to monitor study progress and address any issues arising including those related to potential problems (below), although risk of these is considered very low.

Screening and Follow up Sessions: Participants may feel uncomfortable with the laboratory environment; thus, care will be taken with familiarising them with the researchers, the set up and methods of the study. Participants may be uncomfortable with male or female researchers. To mitigate potential for participants to feel uncomfortable in the research environment they will be informed they are welcome to bring a support person to the laboratory. Other potential problems related to specific outcome measures have been described previously.

Participants will also be informed that in the unlikely event any symptoms resulting from attending the screening session, any of the treatment sessions or the follow up sessions does not subside, or they are concerned that the pain may re-appear, they will be welcome to contact the primary investigator ([name]). If any unresolved concern persist, referral to a GP or physiotherapist of their choice will be considered. If there is lingering pain or symptom reproduction as a result of the study, they will be informed that they may be able to seek an ACC claim to cover treatment of the pain.

Adverse event management: The risk of any adverse event is minimal. In case a participant presents with an adverse event, report to the internal Health & Safety Committee (Centre for Health, Activity and Rehabilitation Research—University of Otago) will be made immediately by the PI (OG) to assess whether reporting the adverse event to the study sponsor, and the Ethics Committee is necessary. If more than one serious adverse event of any kind occurs and if these are related or caused by the treatment interventions, we will suspend the study. If the cause of the events cannot be determined or remediated, and is plausibly related to the intervention, the study will be terminated.

Funding:

The School of Physiotherapy, University of Otago, is providing the laboratory and GST costs associated with running the project. Project expenses including cost of equipment for the SPE, physiotherapy treatment costs, participant/ health care practitioner reimbursement for time, focus group and interview costs including refreshment and transcription will be funded by the PI's Stanley Paris Fellowship Award (\$99 986 NZD) and S fund.

Timeline

Project	PLANNED TASK	2023												2024				
		M	A	M	J	J	A	S	O	N	D	J	F	M	A	M	J	J
Ethics	Ethical Approval																	
Feasibility Study	Finalise Feasibility Study Protocol																	
	Recruit Study Coordinator																	
	Treating Physiotherapist Training																	
	Participant recruitment/ Data Collection																	
	Data extraction and analysis																	
	Data Extraction / Thematic Analysis																	
	Abstract and Manuscripts writeup and submission																	
	Treatment Outcomes Pilot Study	Statistical Analysis																
Abstract writeup																		
Abstract submission IFOMPT 2024/ AAOMPT 2024																		
Manuscript Preparation - Treatment Outcomes Study																		
Manuscript Submission - Treatment Outcomes Study																		
Preliminary Analysis of treatment outcome data																		
Additional Study Objectives		Grant Preparation and Submission using pilot outcome data - Emerging																

	Researcher First Grant																	
--	---------------------------	--	--	--	--	--	--	--	--	--	--	--	--	--	--	--	--	--

References

1. Schneider, K.J., et al., *Rest and treatment/rehabilitation following sport-related concussion: a systematic review*. Br J Sports Med, 2017. **51**(12): p. 930-934.
2. Babcock, L., et al., *Predicting postconcussion syndrome after mild traumatic brain injury in children and adolescents who present to the emergency department*. JAMA Pediatr, 2013. **167**(2): p. 156-61.
3. Iverson, G., et al., *Predictors of clinical recovery from concussion: a systematic review*. BJSM, 2017. **51**(12): p. 941-948.
4. Langevin, P., et al., *Cervicovestibular Rehabilitation in Adults with Mild Traumatic Brain Injury: A Randomized Clinical Trial*. J Neurotrauma, 2022. **39**(7-8): p. 487-496.
5. Kennedy, E., et al., *Can the Neck Contribute to Persistent Post-Concussion Symptoms? A Prospective Descriptive Case Series*. J Orthop Sports Phys Ther, 2019: p. 1-31.

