This may be due to several factors. Firstly, evidence shows that post-concussion symptom profiles are similar regardless of injury phenotype [7]. For e.g., headache, dizziness and neck pain are among the most frequently reported symptoms [8]. However, these symptoms are common across multiple systems that may become impaired following concussion including the oculomotor, vestibular, physiological (migraine), and cervical spine musculoskeletal and sensorimotor systems [9]. Secondly assessment to determine which systems require specific treatment approaches is necessarily broad [10, 11] which is time consuming, expensive, and may result in symptom exacerbation for days afterwards. Thirdly, because it may take review by several health service providers to identify optimal management strategies for a patient, additional costs may be incurred. This may impact accessibility to concussion management services and may mean that not all concussed individuals are treated as quickly or effectively as they could be, while others may not be able to access appropriate treatment due to limited financial or logistical resources. This inaccessibility to appropriate treatment within an expedited time frame may therefore be contributing to the high rate of PPCS.

An urgent need therefore exists to identify ways to streamline the process by which acutely concussed individuals are directed to optimal treatment plans. Any model implemented would however need to fit within the framework of existing local concussion management strategies. Recent cluster and descriptive analyses [9, 12] have identified preliminary evidence for use of a simplified physical exam (SPE) to identify individuals suited to cervical spine Orthopedic Manual Treatment (OMT) and neuromuscular/sensorimotor retraining. Identification is based on positive tests on 2 out of 3 specific cervical spine musculoskeletal outcomes, and at least 1 sensorimotor outcome, as well as an absence of 2 or more positive oculomotor indicators of vestibulo-ocular impairment. Time to perform this SPE is significantly less than that taken for physical exams performed by varying health service providers collectively. This may contribute to expedited plans that effectively manage individual injuries. Additionally, if effective, reductions in risk of developing PPCS and improved equity of access to suitable treatment may be possible.

Study Objectives:

The specific objective of the research project for this application are:

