Volunteers who: respond to advertisement i) using the online screening questionnaire relating to the inclusion/exclusion criteria (primarily whether they have sustained a medically diagnosed concussion within the last 14 days); ii) the study phone; iii) the study email, or who are referred by a health practitioner will be contacted by the study SC. The SC will further screen them for inclusion and exclusion criteria. If eligible to participate in the screening session participants will be forwarded an electronic participant information sheet and consent form and scheduled for the screening session. Individuals contacting the SC in response to advertising who meet exclusion criteria at any stage of the screening process will be provided with names and contact details of primary health services for concussion in Dunedin for follow up if desired. Those recruited via advertisement will be requested to obtain written confirmation of their concussion from their treating physician.

Inclusion criteria: Adults aged 18-60 years, biological sex: male, female, who have sustained a medically diagnosed concussion (mild Traumatic Brain Injury) based on published diagnostic criteria [13-15] and are not more than 14 days since injury [14].

Exclusion criteria: Individuals with past or current history of:

- Moderate to severe TBI as defined by published diagnostic criteria [16]
- Diagnosed concussion with associated trauma related abnormalities apparent on CT or MRI and/ or cervical spine fracture
- Diagnosed concussion due to assault
- Neck pain unrelated to concussion injury(/ies) (requiring treatment)
- Headache disorders (including cervicogenic, migraine (chronic), and tensions type headaches)
- Vestibular, oculomotor, neurological disorders
- Major psychiatric disorders currently being actively treated
- Physical injury that would prevent completion of the screening session

Study power:

Based on previously identified rates of neck impairment post-concussion [9, 17] it is anticipated that screening of **160** participants will be required to identify **60** individuals who meet inclusion criteria. Allowing for 50% of individuals to decline participation in the trial and a 10% drop-out rate, it is anticipated that data from **n=27** participants (treatment commenced with **n=30**) will be collected at all data collection time points. This group size is consistent with those currently used in randomised control trials investigating outcome following OMT of the

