At the screening session, the project will first be explained to the potential participants and their questions answered before signing the consent form (Consent form A – Patients). If they do not agree to participate, the electronic questionnaire data will be deleted, and no further use will be made of it. Women will be asked to wear a sports bra or a singlet that exposes the neck region fully. Men will be asked to remove their shirt or wear a singlet that also exposes the neck fully. Anthropometric measures (height, weight, and neck girth) will then be measured.

Simplified Physical Examination:

Measures of cervical spine function: including kinematic assessment [30], neck flexor endurance [31], manual spinal examination [32], joint position sense [33], and global head and eye motion accuracy [34, 35] will be conducted during the screening session and will be used to identify presence of neck impairments [12]. Results indicative of positive findings for each outcome will be based on published criteria [9, 32]. Prior to performance of the measures of cervical spine function a quick safety screen in line with current standards of practice internationally and in New Zealand [36, 37] will be performed for all participants attending the screening session. While it is unlikely individuals medically diagnosed with concussion will present with indicators of serious spinal or vascular pathology of the neck (red flags) precautionary evaluation will be undertaken. In the unlikely event signs or symptoms of serious pathology are evident assessment will cease and the participant will be referred for further medical review according to current standards of practice [36, 37].

Description of cervical spine assessments are as follows:

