Participants identified as eligible for entry to treatment arm: will include those participants who demonstrate positive findings for a minimum of 3 cervical spine musculoskeletal and or sensorimotor outcome [12] as well as an absence of 2 or more positive oculomotor indicators of vestibulo-ocular impairment [55, 57]

Participants identified as ineligible for entry to treatment arm: identified due to an absence of sufficient positive neck related physical assessment findings, or alternately a positive

vestibulo-ocular screen will be provided with standardised graduated return to activity information [14, 70] as well as appropriate referral where evidence of vestibulo-ocular or physiological impairment is identified by the SC.

Of note, the SC conducting the laboratory-based screening session will be a New Zealand registered physiotherapist, and hold a current annual practicing certificate, Physiotherapy New Zealand membership, and ACC registration. They will hold additional training in OMT with a minimum of 3 years clinical experience. They will also have received specialised training from the PI (OG) in assessments to be used during the screening session including performance of testing, data reduction, and analysis of quantifiable outcomes necessary to establish participant eligibility for enrolment in the treatment arm of the study.

Estimated duration of total testing time will be 1.25 hour (1 hour for the SPE and 0.25 hours for induction and consent). All participants who provide consent and complete the SPE will be provided with a \$40 voucher to recognise the reasonable costs involved with participating in this study.

Treatment Sessions:

Treatment sessions procedure:

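### The neck part of the SPE rule is stated in two ways that classify some patients oppositely, and the entry criterion is the looser of the two

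*Protocol*

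**What the plan says.** The Background of the Protocol introduces the SPE and cites its sources: "Recent cluster and descriptive analyses [9, 12] have identified preliminary evidence for use of a simplified physical exam (SPE". It then gives the neck rule: "Identification is based on positive tests on 2 out of 3 specific cervical spine musculoskeletal outcomes, and at least 1 sensorimotor outcome". A positive result therefore needs findings in both domains.

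The section Eligibility for Entry to Treatment Arm decides who is treated. It asks for "positive findings for a minimum of 3 cervical spine musculoskeletal and or sensorimotor outcome [12", with no minimum in either domain. The vestibulo-ocular condition is the same in both sections ("as well as an absence of 2 or more positive oculomotor indicators of vestibulo-ocular impairment"), so the difference lies only in the neck component. Both sections cite reference 12. Neither says that the entry rule departs from the Background rule or is meant to be equivalent to it.

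The neck measures are listed under Simplified Physical Examination: "kinematic assessment [30], neck flexor endurance [31], manual spinal examination [32], joint position sense [33], and global head and eye motion accuracy [34, 35". The Protocol does not assign each one to a domain in the entry rule.

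The Study power section gives the expected yield: "screening of 160 participants will be required to identify 60 individuals who meet inclusion criteria". It rests this on published rates of neck impairment (references 9 and 17) and names neither version of the rule.

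**The concern.** The SPE is the object of study, not just a gate into it. Objective 2 seeks preliminary evidence that the SPE picks out people suited to manual treatment and sensorimotor retraining, judged by their response to treatment over time. Part 1 estimates the combined effect of assessing with the SPE and treating those it selects, and the results are to inform a later randomised trial. If the rule applied at entry is not the rule in the rationale, the response observed belongs to a broader group than the one the cited evidence is said to describe. A reader would not know which version of the SPE had been tested.

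The eligible fraction is itself a reported feasibility result. A yield of 60 from 160 can be compared with what is observed only if it is known which rule it was planned for.

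**Working it through.** **1. The plan's own figures.** 60/160 = 37.5% eligible; 60 × (1 − 0.50) = 30 start treatment; 30 × (1 − 0.10) = 27 with data at all time points. The funnel reproduces exactly. The 37.5% cannot be rebuilt, because the rates it rests on are not given.

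**2. Inputs for comparing the rules.** From the list under Simplified Physical Examination I take three musculoskeletal tests (kinematics, flexor endurance, manual examination). There are two or three sensorimotor tests: joint position sense, plus head and eye motion accuracy counted as one or as two. This allocation is my reading. Let M and S be the numbers of positive tests in each domain.

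- Background rule (A): M ≥ 2 and S ≥ 1.
- Entry rule (B): M + S ≥ 3.

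**3. Counting patterns.** M ≥ 2 can occur in 3 + 1 = 4 ways.

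- 3 + 3 tests: A = 4 × (8 − 1) = 28 of 64; B = 20 + 15 + 6 + 1 = 42 of 64.
- 3 + 2 tests: A = 4 × (4 − 1) = 12 of 32; B = 10 + 5 + 1 = 16 of 32.

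A implies M + S ≥ 3, so every A pattern is also a B pattern. The patterns admitted by B alone are:

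| M | S | Patterns, 3 + 3 | Patterns, 3 + 2 |
|---|---|---|---|
| 3 | 0 | 1 | 1 |
| 1 | 2 | 9 | 3 |
| 1 | 3 | 3 | – |
| 0 | 3 | 1 | – |
| Total | | 14 (= 42 − 28) | 4 (= 16 − 12) |

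**4. Illustrative share affected.** Pattern counts are not patient counts, and the Protocol gives no positivity rates. I assume one common rate p for every test and ignore the vestibulo-ocular exclusion.

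For independent tests, P(A) = P(M ≥ 2) × P(S ≥ 1). At p = 0.40, P(M ≥ 2) = 3(0.16)(0.6) + 0.064 = 0.352.

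- 3 + 3: P(A) = 0.352 × (1 − 0.216) = 0.276; P(B) = 0.456; share of B failing A = 1 − 0.276/0.456 = 39%. Out of 160: 44 against 73.
- 3 + 2: P(A) = 0.352 × (1 − 0.36) = 0.225; P(B) = 0.317; share = 29%. Out of 160: 36 against 51.

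With a one-factor latent normal model for correlated tests, the share of B entrants who fail A is:

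| p | 3 + 3, correlation 0 / 0.2 / 0.4 | 3 + 2, correlation 0 / 0.2 / 0.4 |
|---|---|---|
| 0.30 | 44% / 36% / 29% | 32% / 26% / 21% |
| 0.40 | 39% / 32% / 25% | 29% / 23% / 18% |
| 0.50 | 33% / 27% / 21% | 25% / 20% / 15% |

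This gives about 15% to 45%. It is not a bound: with independent tests positive in 30% (musculoskeletal) and 60% (sensorimotor), the share is 47% for 3 + 2 and 64% for 3 + 3.

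**5. What the yield could mean.** Still with equal, independent rates: if 37.5% is the yield under A, B would admit about 80 (3 + 2) to 93 (3 + 3) of 160. If it is the yield under B, A would admit about 43 (3 + 2) to 35 (3 + 3). Halving for refusals gives about 22 to 18 starting treatment, and 10% drop-out leaves about 19 to 16, against 30 and 27 planned.

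**The case against.** The best reply is that the entry rule is loose shorthand. The Background minimum of two plus one also totals three, both sections cite reference 12, and only the eligibility section governs entry. The rules are nested, so everyone positive under the Background rule is still admitted and can be picked out afterwards from the SPE results. The study is a single-group feasibility study that seeks only preliminary evidence on selection. Much of this stands: the information is recoverable at the price of a smaller subset, and the drafters may have intended a single rule. But the text does not say so. As written, staff who score eligibility would admit patients whom the definition of the SPE excludes.

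Three stronger readings are tempting and are not supported.

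- A reader might infer that the two rules select separate populations. They do not; one contains the other.
- A reader might infer that a single virtual-reality assessment could supply all three positives, because five outputs of that device appear in the table under Experimental Outcomes. That table lists exploratory measures and is not the eligibility list. The SPE section names its measures test by test and then speaks of positive findings for each outcome, so an outcome there most naturally means a test.
- A reader might infer that the planned yield belongs to the Background rule and is therefore wrong. The Study power section names neither rule, shares only reference 9 with the Background and does not cite reference 12.

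**Conclusion.** The contradiction is in the text and needs no assumption: patients with three musculoskeletal and no sensorimotor positives, or one and at least two, are eligible under one section and not identified under the other. If three sensorimotor tests count, so are patients with none and three. The entry rule is strictly the looser. The size in patterns is 28 against 42 of 64, or 12 against 16 of 32, given the allocation of tests to domains set out above.

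The size in patients is unknown. The 15% to 45% rests on assumed equal positivity of 30% to 50%, correlations of 0 to 0.4 and no vestibulo-ocular exclusion; it shows direction and scale only. The recruitment arithmetic is correct, and the point on yield is limited to this: 37.5% is tied to neither rule. The consequence for Objective 2 is that the treated group may not be the one the rationale describes. The documents do not settle which rule is right, and this review takes no position on it.

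**What to change.** Before the first screening:

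- Reconcile the Background and Eligibility for Entry to Treatment Arm to one rule, in the same words in both places.
- List the tests that count in each domain and state that each counts once. Say whether head and eye motion accuracy is one test or two.
- State in Study power which rule the 37.5% yield refers to, and revise the funnel if it refers to the other one.
- Report how many screened and how many treated participants are eligible under each version, using the per-test results, with the vestibulo-ocular condition applied in both.

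The cost is a short protocol correction and one extra table. The SPE is already done on everyone screened and clinical data go into the study's recording form, so no new measurement is needed; the form should hold a positive or negative result for every counted test.
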